#### **Summary of Other Efficacy Measures**

Urinary tract infection/urosepsis, urinary incontinence, and renal insufficiency are captured as potential BPH disease related events; reference Section 7.2.1.2. Frequencies of each event will be presented by treatment group; no formal treatment comparisons are planned.

#### 9.3.7.2. Safety Analyses

The Intent-to-Treat population will be used for the analysis of safety data. Complete details of the safety analyses will be provided in the RAP.

## **Extent of Exposure**

Study drug exposure in days will be calculated for each subject as treatment stop date minus treatment start date plus one and will be summarized by treatment group. Study drug compliance between visits and cumulative study drug compliance will be calculated by dividing the number of study drug capsules used by the total number of study drug capsules prescribed and multiplying the result by 100. Study drug compliance between visits and cumulative study drug compliance will be summarized by treatment group.

#### **Adverse Events**

Adverse events (AEs) will be coded using Medical Dictionary for Regulatory Activities (MedDRA). The frequency of events, the frequency of subjects and the percentage of subjects reporting each adverse event will be summarized by treatment group for all AEs and separately for drug-related AEs. The proportion of subjects reporting at least one AE, at least one drug-related AE, at least one serious AE, and at least one AE leading to withdrawal will be computed for each treatment group. Comparisons of treatment groups for each of these sets of AEs will be performed using Fisher's exact test.

Special interest adverse events will be defined in the RAP.

The incidence of deaths and the primary cause of death will be summarized.

#### **Clinical Laboratory Evaluations**

For purposes of statistical analyses, the final value of the laboratory test prior to the start of the randomized treatment will be used as the baseline value. Only those laboratory tests with a numeric normal range and at least one post baseline value will be analysed statistically.

A laboratory value that is on or within the normal range is considered normal. A laboratory value that is outside the testing laboratory's normal range is considered an abnormal laboratory value. A laboratory value that is above the upper limit of the normal range is considered high abnormal. A laboratory value that is below the lower limit of the normal range is considered low abnormal.

To describe the laboratory values at baseline, the frequency of subjects with an abnormal laboratory value at baseline among subjects with a baseline laboratory value and a post baseline laboratory value will be computed by treatment group. Among subjects with a normal value at baseline, the frequency of abnormal values, high abnormal values, and low abnormal values at any post baseline laboratory will be computed by treatment group. Among subjects with a normal or low abnormal value at baseline, the frequency of high abnormal values at any post baseline will be computed by treatment group. Among subjects with a normal or high abnormal value at baseline, the frequency of low abnormal values at any post baseline laboratory will be computed by treatment group.

The threshold laboratory values are defined in terms of a multiplicative factor of the testing laboratory's normal range. A laboratory value that is above the upper limit factor multiplied by the upper limit of the normal range is considered a high threshold value. A laboratory value that is below the lower limit factor multiplied by the lower limit of the normal range is considered a low threshold value.

To describe the laboratory values at baseline, the frequency of subjects with a threshold laboratory value at baseline among subjects with a baseline laboratory value and a post baseline laboratory value will be computed by treatment group. Among subjects whose baseline value was not classified as threshold, the frequency of subjects with threshold values at any post baseline laboratory will be computed by treatment group. Among subjects whose baseline value was not high threshold, the frequency of subjects with high threshold values at any post baseline laboratory will be computed by treatment group. Among subjects whose baseline value was not low threshold, the frequency of subjects with low threshold values at any post baseline laboratory will be computed by treatment group.

Differences in laboratory values between baseline and the final scheduled laboratory assessment will be calculated for each laboratory test and summarized by treatment group.

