## 7.2.2.5. End of Study Treatment Assessments

During the study period that is between the scheduled visits, if a subject discontinues study treatment permanently after Visit 2 (post-randomisation) for any reason, other than lost to follow-up, the investigator should make every effort to schedule a visit by the subject to the study site and complete the following assessment:

- Concomitant medications
- Adverse events
- Physical exam including vital signs, DRE and qualitative breast examination
- Obtain blood samples for hematology, clinical chemistry and PSA determinations
- Administer health outcome questionnaires (IPSS, BHS,BII and PAS-SFI)
- Administration of C-SSRS questionnaire
- Record any episodes of AUR, and, BPH-related prostatic surgery or minimally-invasive/non-surgical interventions
- Record any episodes of UTI/urosepsis, urinary incontinence (first episode or consistent worsening), and renal insufficiency
- Retrieve any unused double-blind study medication, assess compliance and record date of last dose of study medication
- Discuss the biannual follow-up phone call schedule
- Complete subject eCRF

If the decision for a subject's study treatment discontinuation is made during a regularly scheduled visit, the procedure that are stated above should be completed, in addition to any scheduled procedure that is not listed above.

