## 7.3.4. Clinical Laboratory Assessments

Blood samples for all laboratory assessments throughout the study will be collected prior to undergoing any clinical procedures. In order to determine each subject's eligibility to participate in the study, the results of the screening clinical laboratory tests must be assessed by the principal investigator or designee prior to study drug administration. Any

subject having a laboratory result that falls outside the specifications noted in the inclusion or exclusion criteria will be excluded from the study.

Out-of-threshold range values indicated on the clinical laboratory test reports must be assessed as "not clinically significant" (NCS), "clinically significant" (CS), or "repeat" (to indicate a repeat test will be performed). If any laboratory values are deemed clinically significant, the subject must return to the clinic for re-evaluation. All clinically significant changes from baseline will be followed until resolution or stabilization as determined by the principal investigator or designee. The results of all clinical laboratory tests must be assessed by the investigator in order to determine each subject's eligibility to continue in the study.

Haematology and clinical chemistry assessments will be performed at Pre-screening (Visit 1a) to establish eligibility for enrolment and annually post-randomisation at Visits 6, 10. Additionally, a blood draw for HBsAG, and Hepatitis C Antibody should be performed at Visit 2 (baseline).

Laboratory Assessment	Visit Frequency
Hematology	Visits 1a,6, 10
Clinical Chemistry	Visits 1a, 6, 10
PSA	Visits 1a, 4, 6, 10
HBsAG and Hepatitis C Antibody	Visit 2

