## 9.2. Study Design Considerations

## 9.2.1. Sample Size Assumptions

The sample size was calculated based on estimates of IPSS change from baseline using information obtained from the CombAT study. Sample size estimates were computed in terms of a continuous response variable assuming a normal distribution, IPSS change from baseline mean difference between treatment groups of 1.8, a standard deviation of 6, and considering 90% power. With these assumptions, the required minimum sample size is 234 subjects per arm. Therefore, since a 20% treatment phase discontinuation rate is assumed, then randomization of 293 subjects per treatment arm (586 total) is required for 90% power.

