## 9.3.4. Analysis Data Sets

Endpoints measured at specific visits and analysed in terms of visit numbers include: IPSS, Qmax, prostate volume, PSA, post void residual volume, suicidality and health outcomes. Analysis of the data collected in terms of visit numbers will be performed using two different approaches to account for missing data.

- 1. LOCF (Last Observation Carried Forward) analysis: This involves bringing (carrying) forward the last non-missing post-baseline assessment for subjects with missing visit data and/or for subjects who discontinued from the study.
- 2. At Visit analysis: Missing values at post-baseline assessments are not replaced and are regarded as missing.

The LOCF approach will be considered primary. If the LOCF and At Visit results are not consistent with regard to the statistical analyses and conclusions, then further data analyses will be undertaken.

Endpoints measured in terms of event calendar days and analyzed in terms of survival methodology include AUR and BPH-related surgical intervention. These analyses will use the observed-cases approach in which actual date of event is used; missing values post-baseline are not replaced and are regarded as missing.

Analysis datasets will be created with a structure to reflect the above noted approaches for each endpoint.

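### Laboratory change is summarised only to the final scheduled assessment, which read literally leaves men who stop early out of that one descriptive table although their end-of-treatment bloods are requested

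*Protocol*

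**What the plan says.** Clinical laboratory measurements are a listed safety endpoint (Protocol section 7.3.1). Under Clinical Laboratory Evaluations in section 9.3.7.2, the quantitative change summary is fixed in one sentence: "Differences in laboratory values between baseline and the final scheduled laboratory assessment will be calculated", test by test and reported by arm. No test or model is attached to it.

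Section 7.3.4 schedules haematology and chemistry at pre-screening (Visit 1a) and then "annually post-randomisation at Visits 6, 10".

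For a man who permanently stops treatment after randomisation, section 7.2.2.5 lists, among the End of Study Treatment assessments: "Obtain blood samples for hematology, clinical chemistry and PSA determinations". Appendix 2 repeats this. Both set that visit in the interval between scheduled visits. Section 6.3 plans nothing after it except telephone contact every six months.

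Section 9.3.4 gives the endpoints analysed by visit, under LOCF (last observation carried forward) and At Visit handling. They "include: IPSS, Qmax, prostate volume, PSA, post void residual volume, suicidality and health outcomes". Haematology and chemistry are not named.

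Section 9.3.7 states in general terms that all data up to completion or withdrawal enter the analysis, however long the subject was treated.

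**The concern.** The protocol asks for a laboratory sample when a man stops treatment, but the sentence defining the change summary points to a scheduled visit that he will not attend. As written, that summary describes men who reached Month 24. The abnormal and threshold frequencies in the same section accept any post-baseline result. Two laboratory tables set side by side would therefore rest on different sets of men, and nothing requires the report to show it.

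Adverse events are one of the listed reasons for stopping (section 4.2.1), so it cannot be presumed that men who stop resemble completers in laboratory change. A mean change restricted to completers describes a selected group and should be labelled as such, or set beside a summary that includes the others.

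**Working it through.** **Inputs**
- 293 men per arm and 586 in total: "randomization of 293 subjects per treatment arm (586 total) is required for 90% power" (section 9.2.1).
- Discontinuation: "since a 20% treatment phase discontinuation rate is assumed" (section 9.2.1).
- Planning values: difference 1.8, SD 6, power 90% (section 9.2.1); two-sided alpha 0.05 (section 9.1).
- Post-baseline laboratory visits: 6 and 10 (section 7.3.4).

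**Reproducing the plan's own figures**
- A two-sample comparison of means with difference 1.8, SD 6, two-sided alpha 0.05 and 90% power needs 234 men per arm, as stated.
- Inflation for discontinuation: 234 / (1 − 0.20) = 292.5, rounded up to 293 per arm; 2 × 293 = 586. This agrees.

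**Which assessment is the final scheduled one**
- Of the two post-baseline laboratory visits, Visit 10 is the later.
- Section 9.3.7.2.1 uses nearly the same expression for PSA, as the point from which the treatment comparisons begin. There it can only mean a study visit, not each man's own last value.
- The End of Study Treatment visit is described as lying between scheduled visits, so on the protocol's own terms its bloods are not a scheduled assessment.

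**Whether another rule brings the discontinuers in**
- For PSA and post-void residual volume, section 9.3.7.2.1 expressly applies both LOCF and At Visit. The laboratory text in section 9.3.7.2 does not.
- The list in section 9.3.4 is introduced by a word that leaves it open. The absence of haematology and chemistry is therefore suggestive, not conclusive.
- The inclusion statement in section 9.3.7 does not say which value counts as final. Taken literally, it and the laboratory sentence pull in different directions.

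**Men without a Visit 10 value under the literal reading**
- Per arm: 0.20 × 293 = 58.6, about 59.
- Total: 0.20 × 586 = 117.2, about 117, leaving 586 − 117 = 469.
- Over an assumed range of 10% to 30% discontinuation: 0.10 × 586 = 58.6 to 0.30 × 586 = 175.8, about 59 to 176 men in total.

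**Effect on the reported mean**
- With a fraction 0.20 absent, the completer mean differs from the full-arm mean by 0.20 × (completer mean change − discontinuer mean change).
- The protocol gives no value or sign for the bracket, so neither the size nor the direction of a bias can be computed.

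**The case against.** The strongest reply is that the exclusion is inferred, not stated. The sentence does not name Visit 10. Footnote i to the Time and Events Table says that the Visit 10 column also serves the End of Study Treatment assessments, and section 9.3.7 includes all data. Together these allow the end-of-treatment sample to stand as a man's final assessment. Section 9.3.7.2 also leaves full safety details to the reporting and analysis plan, where visit assignment of early-discontinuation samples is usually settled.

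Part of this stands: the wording is ambiguous. But the footnote governs which procedures are performed, not which value is analysed. The two visits are not identical either: the section 7.2.2.5 list omits transrectal ultrasound, Qmax and residual volume unless the decision to stop falls at a scheduled visit. The protocol has also already chosen the time point, so an analysis plan using the last value would depart from this sentence, and section 9.3.7 requires departures to be documented.

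The objection succeeds fully on impact. A reader might infer that discontinuers' laboratory results drop out of the safety evaluation. They do not: any post-baseline result feeds the abnormal and threshold frequencies, where a man stopping for abnormal chemistry would appear. A reader might also infer that a treatment contrast is biased, but the protocol specifies no test of laboratory change.

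**Conclusion.** The point holds in a narrow form. Read literally, the sole quantitative change summary for haematology and chemistry covers about 469 of 586 men and leaves out about 117, roughly 59 per arm, while the protocol requests bloods from men who stop and says elsewhere that all data are used.

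The count rests on two assumptions: that the planned 20% treatment discontinuation occurs, and that a man who discontinues has no Visit 10 sample. The 20% is a planning figure, not an observed number of missing results.

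It is tempting to conclude that the mean changes are biased towards no effect. The documents do not support that. It would require discontinuers to show larger changes than completers, and nothing in the protocol establishes this or its size. Nor can it be said that every discontinuing man supplies a last on-treatment value. Section 7.2.2.5 excepts men lost to follow-up and asks only for best efforts, section 6.3 lets a man decline further contact, and the visit takes place after treatment has stopped.

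The primary endpoint, sample size, power and alpha are unaffected. This is an inexpensive clarification of a descriptive safety table.

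**What to change.** Under Clinical Laboratory Evaluations in section 9.3.7.2, add a summary by treatment group of change from baseline to the last post-baseline laboratory assessment, stating that this includes the End of Study Treatment sample where one was obtained. Present it beside the change to Visit 10, name that visit explicitly, and add the change to Visit 6, for which the protocol specifies no laboratory change summary. Show the number of men contributing to each.

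The cost is a sentence or two of text and extra rows in the laboratory tables. The samples are already requested, so no procedure is added.

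There are two limits. A last-value change mixes different exposure durations, which is why the by-visit changes belong next to it. Men lost to follow-up or refusing the end-of-treatment visit are recovered only through a Visit 6 value, if they have one, so the last-value summary may still fall short of 586. The protocol does not allow that shortfall to be estimated.

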#### 9.3.7.2.1. Other Safety Measures

#### Serum PSA

Total PSA, change from baseline total PSA, and percentage change from baseline total PSA will be summarized by treatment group using both the LOCF and At Visit approaches at each scheduled post-baseline assessment.

Change from baseline total PSA will be compared at each scheduled post-baseline assessment using a general linear model with effects for treatment and baseline total PSA. Statistical analysis of the change from baseline total PSA comparing the treatment groups will begin using data from the final scheduled assessment. Abnormalities at any assessment will be listed by treatment and subject.

#### Post Void Residual Volume

RM2010/00134/05

Post void residual volume, change from baseline post void residual volume, and percentage change from baseline post void residual volume will be summarized using both LOCF and At Visit approaches at each scheduled post-baseline assessment. Treatment groups will be compared in terms of the change from baseline distribution at each post baseline visit using a nonparametric van Elteren test controlling for cluster.

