#### 4.1.3. Exclusion Criteria

Subjects meeting the following criteria must not be enrolled in the study:

*Medical Condition Exclusions:* 

1. History or evidence of prostate cancer (e.g. positive biopsy or ultrasound, suspicious DRE). Patients with suspicious ultrasound or DRE who have had a negative biopsy within the preceding 6 months and stable PSA are eligible for the study.

Note: If total serum PSA is >4ng/mL and unless PSA value has been stable for at least the past 2 years, the investigator should make every appropriate effort to exclude the possibility of prostate cancer, including consideration of prostate biopsy.

- 2. Previous prostatic surgery (including TURP, laser, HIFU (transrectal high intensity focused ultrasounds), thermotherapy, TUNA, (transurethral needle ablation), balloon dilatation, and stent replacement) or other invasive procedures to treat BPH.
- 3. History of flexible/rigid cystoscopy or other instrumentation of the urethra within 7 days prior to the Screening Visit. Catheterisation (<10F) is acceptable with no time restriction.
- 4. History of AUR within 3 months prior to Screening Visit.
- 5. Post-void residual volume >250mL (suprapubic ultrasound) at Screening.
- 6. Any conditions other than BPH, which may in the judgment of the investigator, result in urinary symptoms or changes in flow rate (e.g. neurogenic bladder, bladder neck contracture, urethral stricture, bladder malignancy, acute or chronic prostatitis, or acute or chronic urinary tract infections).
- 7. Unstable liver disease (chronic stable hepatitis B and C are acceptable if subject meets entry criteria).
- 8. History of renal insufficiency, or serum creatinine >1.5 times the upper limit of normal at Screening.
- 9. Any unstable, serious co-existing medical condition(s) including, but not limited to:
- a. Myocardial infarction, coronary bypass surgery, unstable angina, cardiac arrhythmias, clinically evident congestive heart failure, or cerebrovascular accident within 6 months prior to Screening visit; uncontrolled diabetes or peptic ulcer disease which is uncontrolled by medical management.
- b. Postural hypotension, dizziness, vertigo or any other signs and symptoms of orthostasis, which in the opinion of the investigator could be exacerbated by tamsulosin and result in putting the subject at risk of injury.

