## 7.3.5. Post Void Residual Volume

Post void residual volume will be measured suprapubically by ultrasound (immediately following the urinary flow measurement) at Pre-screening Visit 1a/1b (if Qmax inclusion criteria not met at Visit 1A), at Baseline (Visit 2) and at 26 week clinic visits thereafter during the treatment period. Subjects with post void residual volumes >250mL as

2016N305272\_00 ARI114265

measured at Screening (Visit 1a/1b) should be excluded from participating in the study. The time of bladder scan and the time of the preceding void will also be recorded.

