## 9.3.7.1. Efficacy Analyses

#### **Primary Analysis**

The primary efficacy parameter after two years of study treatment is change from baseline IPSS. Symptom improvement is measured using the IPSS and evaluated using change from baseline.

Total IPSS, change from baseline IPSS, and percentage change from baseline IPSS will be summarized by treatment group using both the LOCF and At Visit approaches at each scheduled post-baseline assessment. Change in baseline IPSS will be compared at each scheduled post-baseline assessment for combination therapy versus 0.2mg tamsulosin using a general linear model with effects for treatment, cluster, and baseline IPSS at alpha=0.05.

CONFIDENTIAL

Missing individual responses for the IPSS questionnaire will be imputed as defined in Section 9.3.7.

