#### **Secondary Analyses**

The year 2 secondary efficacy endpoints include: Qmax; prostate volume; IPSS improvement of  $\geq 2$  points,  $\geq 3$  points and, separately,  $\geq 25\%$  improvement from baseline; and Qmax improvement of  $\geq 3$ ml/sec and, separately,  $\geq 30\%$  improvement from baseline. Time to AUR or BPH-related surgical intervention is also a secondary efficacy endpoint.

The following describes the year 2 secondary efficacy endpoints and associated analyses. All treatment comparisons referenced are in terms of the combination therapy versus 0.2 mg tamsulosin.

 Prostate volume, change from baseline prostate volume, and percentage change from baseline prostate volume will be summarized by treatment group using both the LOCF and At Visit approaches at each scheduled post-baseline assessment.
 Percentage change from baseline prostate volume will be compared at each scheduled post-baseline assessment using the following general linear model:

log(post-baseline prostate volume/baseline prostate volume) = log(baseline prostate volume) + treatment + cluster

- Symptom improvement is measured using the IPSS and also evaluated using a categorical change from baseline improvement of ≥2 points and ≥3 points and, separately, ≥25% improvement from baseline. Treatment comparisons will utilise a Mantel-Haenszel test controlling for cluster at alpha=0.05.
- Maximum urinary flow (Qmax), change from baseline Qmax, and percentage change from baseline Qmax will be summarized by treatment group using both the LOCF and At Visit approaches at each scheduled post-baseline assessment. Change from baseline Qmax will be compared at each scheduled post-baseline assessment using a general linear model with effects for treatment, cluster, and baseline Qmax.
- Qmax improvement of ≥3mL/sec and, separately, ≥30% improvement from baseline will be computed by treatment group. Treatment comparisons will utilise a Mantel-Haenszel test controlling for cluster at alpha=0.05.
- Time to first AUR or BPH-related surgical intervention will be defined as the number of days from date of first dose of randomized study drug to date of the first event (earliest occurring of either AUR or BPH-related surgery) for each subject. Censoring will occur at the earliest of the following dates as applicable: the date of prostatectomy, the date of last contact for AUR and surgical intervention assessment,

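### Post-void residual volume is the only continuous visit-based measure formally compared without its baseline in the analysis; the planned test is valid but gives up some efficiency

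*Protocol*

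**What the plan says.** PVR is a listed safety endpoint (7.3.1). Section 7.3.5 schedules it at screening, then "at Baseline (Visit 2) and at 26 week clinic visits thereafter during the treatment period". Subjects are excluded for "Post-void residual volume >250mL (suprapubic ultrasound) at Screening" (4.1.3). Section 9.3.7 defines baseline as the last value before randomised treatment starts.

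The PVR paragraph of 9.3.7.2.1 summarises values, change and percentage change under both the LOCF and At Visit approaches. It then compares the arms on the "change from baseline distribution at each post baseline visit using a nonparametric van Elteren test controlling for cluster". No baseline term appears, and no reason is given for leaving it out.

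The other continuous measures are handled differently:

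- IPSS (9.3.7.1): "using a general linear model with effects for treatment, cluster, and baseline IPSS at alpha=0.05"
- Qmax (9.3.7.1): "general linear model with effects for treatment, cluster, and baseline Qmax"
- Prostate volume (9.3.7.1): "log(post-baseline prostate volume/baseline prostate volume) = log(baseline prostate volume) + treatment + cluster"
- PSA, the neighbouring safety measure in 9.3.7.2.1: "general linear model with effects for treatment and baseline total PSA"
- BHS, BII and PAS-SFI (9.3.7.3): a general linear model with treatment, cluster and the baseline score in each case.

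**The concern.** Subtracting baseline is not the same as adjusting for it. A change score carries the full noise of the baseline reading and usually stays negatively correlated with baseline. An analysis that conditions on baseline removes only the part that predicts follow-up, and so compares the arms with less residual variance.

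The likely skewness of PVR explains the choice of a rank test. It does not explain omitting baseline, because rank methods can adjust for a covariate and still stratify by cluster.

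What is at stake is sensitivity. The trial is sized for IPSS alone (9.2.1). If PVR does differ between arms, the planned test is less likely to show it than the same data allow, and a null result on a safety measure would reassure more than it should.

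**Working it through.** **1. The plan's own figures.** These supply only the sample size used below. With a difference of 1.8, SD 6, two-sided 0.05 and 90% power, n = 2 × (1.960 + 1.282)² × 36 / 3.24 = 233.5, so 234 per arm. Then 234 / 0.80 = 292.5, so 293 per arm. Power at 234 per arm is 82.2%, 90.1% and 95.0% for differences of 1.6, 1.8 and 2.0. All agree with 9.2.1 and 9.2.2. They concern IPSS; the protocol states nothing comparable for PVR.

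**2. Direction.** Let σ₀ and σ₁ be the baseline and follow-up SDs and ρ their correlation.

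- Variance of change: σ₀² + σ₁² − 2ρσ₀σ₁
- Variance after linear adjustment for baseline: σ₁²(1 − ρ²)
- Difference: (σ₀ − ρσ₁)², which is never negative

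So in large samples adjustment does no harm, and it gains nothing only when ρ = σ₀/σ₁. With equal SDs, the ratio of adjusted to change-score variance is (1 − ρ²) / [2(1 − ρ)] = (1 + ρ)/2, which is below 1 for any ρ below 1.

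**3. Size under normal theory.** Assumptions: equal SDs, and two-sided 0.05 (stated for the primary hypothesis, assumed for PVR). If the change-score test has 80% power, adjusted power = Φ[(1.960 + 0.842) / √((1 + ρ)/2) − 1.960]. At ρ = 0.5 this is Φ(2.802 / 0.866 − 1.960) = Φ(1.275) = 89.9%.

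| ρ | Variance ratio | Adjusted power if change has 80% | Change-score power if adjusted has 90% |
|---|---|---|---|
| 0.3 | 0.65 | 93.5% | 74.3% |
| 0.5 | 0.75 | 89.9% | 80.2% |
| 0.7 | 0.85 | 86.0% | 84.8% |

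**4. Size for rank tests, by simulation.** Van Elteren on raw change is compared with van Elteren on within-cluster rank residuals. Assumptions: 234 per arm, 8 clusters, 1,500 runs per setting, and an effect set so that the adjusted test has roughly 85 to 90% power. The skewed case is lognormal (median 40 mL, log-SD 0.8, baseline cut at 250 mL) with the effect on the log scale.

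| ρ | Normal: change → adjusted | Skewed: change → adjusted |
|---|---|---|
| 0.3 | 72.0% → 86.7% | 65.2% → 89.7% |
| 0.5 | 79.3% → 87.3% | 71.7% → 87.3% |
| 0.7 | 84.5% → 85.5% | 77.0% → 86.3% |

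**5. Dependence on the form of the effect.** With a different lognormal (log mean 3.3, log-SD 0.9) at ρ = 0.5, a log-scale shift of 0.20 gave 53% on raw change and 71% adjusted; an additive 5 mL shift gave 51% and 81%. Across such settings with skewed PVR the gain runs from roughly 5 to 35 points.

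**6. Type I error.** Null rejection in the second lognormal set-up was 5.0 to 5.3% for the planned test and 5.0 to 5.9% for the adjusted one.

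**The case against.** The planned test is sound. Under randomisation a van Elteren test on change holds its level, a rank test suits skewed data, and the result can be read against change in mL. This stands in full.

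PVR is also a minor measure here. It is one of seven safety endpoints, it is absent from the comparisons listed in 9.3.5.2, it carries no power claim or decision rule, and its values and changes are summarised anyway. That stands and sets the weight of the point.

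Part of the simulated gain is not due to baseline adjustment. With the log-scale effect at ρ = 0.5, testing the log ratio without any covariate already moved power from 53% to 62%, against 71% for the adjusted rank test. About half of that gap (9 of 18 points) therefore reflects testing raw mL when the effect is proportional. The additive case shows a larger gap without that mismatch, so the size depends on the model in both directions.

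The proposed test has its own limits. It fits a rank slope in each cluster, yet 9.3.7 defines clusters only after randomisation is complete, so their number and size are unknown; 8 is an assumption.

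None of this supplies a reason to ignore a baseline reading that is already collected and that the plan uses for every comparable measure.

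**Conclusion.** The point holds as a minor efficiency and consistency improvement. PVR is the only continuous visit-based measure formally compared without its baseline in the analysis. Conditioning on baseline is at least as efficient in large samples under linear theory, and it was never materially worse in the simulations.

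The size is not fixed by the documents. It rests on an assumed correlation, SDs, effect form, cluster count and reference power. Under normal theory with 80% power for the change score, the gain is about 13, 10 and 6 points at ρ = 0.3, 0.5 and 0.7. With skewed PVR it is roughly 5 to 35 points; with normal data at ρ = 0.7 it can be about 1 point.

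Four stronger readings are not supported:

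- **That PVR is the only inferential comparison without baseline.** The IPSS and Qmax responder tests use Mantel-Haenszel controlling for cluster alone, and the breast and DRE comparisons use Fisher's exact test. Those outcomes are binary; the contrast holds only among continuous measures.
- **That a single figure, such as 15 to 19 points, is lost.** Such a figure fits only particular choices of correlation, reference power and distribution.
- **That the comparison is biased or its error rate inflated.** A chance baseline imbalance can move the observed change in one trial, but the test keeps its level over randomisations.
- **That PVR is the trial's sole view of bladder emptying.** Incomplete emptying is also a listed BPH symptom (7.4.2.5), and acute retention is recorded at every scheduled visit from baseline (7.3.6). PVR is the objective volume measure.

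**What to change.** In the PVR paragraph of 9.3.7.2.1, replace the test on raw change with a rank-based analysis of covariance stratified by cluster. Within each cluster, rank post-baseline PVR and baseline PVR, regress the first ranks on the second, and apply the van Elteren test to the residuals. Keep the planned summaries of change and percentage change, which still report the result in mL.

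The cost is one sentence and a few lines of code, with no new data or visits. The small downside is that the p-value then refers to baseline-adjusted ranks and no longer to raw change in mL. Because the regression is fitted within cluster, clusters should be formed large enough to support it.
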